## 9.6 STUDY DRUG EXPOSURE AND/OR COMPLIANCE

Duration on treatment and cumulative dose received will be calculated for ulixertinib as defined below.

### Part A

- *Number of cycles received* =  
Number of cycles where the patient received at least one dose.
- *Duration of exposure (months)* =  
[(Date of last known treatment dosing with ulixertinib – date of initial dosing with ulixertinib) + 1] / 30.4375
- *Planned cumulative dose (mg)* =  
Number of cycles received x 28 x 2 x 600.
- *Actual cumulative dose received (mg)* =  
Sum of [(number of capsules dispensed – number of capsules returned) x 150].
- *Relative dose intensity* =  
100 x Actual dose intensity / Planned dose intensity, with:
  - Actual dose intensity (mg/day) = Actual cumulative dose received (mg) / Duration of exposure (days).
  - Planned dose intensity (mg/day) = Planned cumulative dose (mg) / Duration of exposure (days).

Summary statistics will be presented for the number of cycles received, duration of exposure, actual cumulative dose, and relative dose intensity, by group and overall for Part A on the FAS.

The number and percentage of patients having at least one dosing interruption or adjustment will be tabulated with the corresponding reason by group and overall for Part A on the FAS. A by-patient listing will be produced.

Part B study drug exposure and compliance will be further described in an updated SAP version once Part A results are available.

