## 14 Appendices

### 14.1 *Schedule of events*

**Table 14.1 Part A and B: Schedule of Activities**

		Cycle 1 Day 1 through 28			Cycle 2 Day 29 through 56			Cycle 3-X 28-day cycles, visit on 1 st day of cycle	Post Treatment Period		
Visit	1 Screening	2 Baseline	3 Tx	4 Tx	5 Tx	6 Tx	7 Tx	8 -X Tx	End of Treatment (EOT) Visit	Safety Follow- Up a	Follow- Up b
Visit Day	-28 to -1	1 ± 0	8 ± 3	15 ± 3	29 ± 3	36 ± 3	43 ± 3	57 ± 3	≤14 ± 3 days after last dose	30 ± 3 days after last dose	
Informed consent	X										
Inclusion/exclusion criteria	X	X									
Demography	X										
Medical history c	X	X	X	X	X	X	X	X	X		
Cancer history d	X										X
Concomitant medications	X	X	X	X	X	X	X	X	X		
Measure height	X										
Measure weight	X	X	X	X	X	X	X	X	X		
Vital signs	X	X	X	X	X	X	X	X	X		
Physical examination e	X										
ECOG	X	X	X	X	X	X	X	X	X		
Ophthalmology exam f	X										
Pregnancy test g,h	X	X g			X h			X h	X h		
Clinical lab tests i,j	X	X i	X	X	X	X	X	X j	X		
Electrocardiogram (ECG) k	X										
ECHO cardiogram or MUGA	X										

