**PROGRAMMING NOTES:**

- Repeat Table 14.1-3.4
- Present concomitant medications.
- Replace footnote 'Prior medication is defined as...' with the following footnote:  
'Concomitant medication is defined as any medication ongoing at first day of study drug or started after first day of study drug up to the end of the on-treatment period.'

Table 14.1-4.1 - Treatment exposure  
Full Analysis Set

	Group 1 N=XX	Group 2 N=XX	Group 3 N=XX	Group 4 N=XX	Group 5 N=XX	Group 6 N=XX	Overall N=XX
Number of cycles received							
[a] - n (%)							
1	XX (XX.X)						
2	XX (XX.X)						
3	XX (XX.X)						
...							
n	XX						
Mean (SD)	XX.XX (XX.XX)						
Median	XX.XX						
Min; Max	XX.X; XX.X						
Duration of exposure to ulixertinib (months) [b] - n (%)							
< 1 month	XX (XX.X)						
1-2 months	XX (XX.X)						
2-3 months	XX (XX.X)						
...							
n	XX						
Mean (SD)	XX.XX (XX.XX)						
Median	XX.XX						
Min; Max	XX.X; XX.X						

[a] Number of cycles received = Number of cycles where the patient received at least one dose.

[b] Duration of exposure (months) = [(Date of last known treatment dosing with ulixertinib - date of initial dosing with ulixertinib) + 1] / 30.4375.

[c] Actual cumulative dose received (mg) = Sum of [(number of capsules dispensed - number of capsules returned) x 150].

[d] Relative dose intensity = 100 x Actual dose intensity / Planned dose intensity. Actual dose intensity (mg/day) is defined as Actual cumulative dose received (mg) / Duration of exposure (days). Planned dose intensity (mg/day) is defined as Planned cumulative dose (mg) / Duration of exposure (days).

Program: (Program name.sas) (run on: DDMMYYYY HH:MM)

Filename: (Specify file name.rtf)

**Sponsor:** BioMed Valley Discoveries

**Protocol:** BVD-523-ABC

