**Statistical Analysis Plan:**

2.0 / 09-Jun-2023

BioMed Valley Discoveries  
Protocol: BVD-523-ABC ('Delivery' / 'Type') - Part X  
Data extraction date: DDMMYYYY

Page 2 of Y

Table 14.1-4.1 - Treatment exposure  
Full Analysis Set

	Group 1 N=XX	Group 2 N=XX	Group 3 N=XX	Group 4 N=XX	Group 5 N=XX	Group 6 N=XX	Overall N=XX
Actual cumulative dose on ulixertinib (mg) [c]							
n	XX						
Mean (SD)	XX.XX (XX.XX)						
Median	XX.XX						
Min; Max	XX.X; XX.X						
Relative dose intensity [d]							
n	XX						
Mean (SD)	XX.XX (XX.XX)						
Median	XX.XX						
Min; Max	XX.X; XX.X						

[a] Number of cycles received = Number of cycles where the patient received at least one dose.

[b] Duration of exposure (days) = (Date of last known treatment dosing with ulixertinib - date of initial dosing with ULISSERTINIB) + 1.

[c] Actual cumulative dose received (mg) = Sum of [(number of capsules dispensed - number of capsules returned) x 150].

[d] Relative dose intensity = 100 x Actual dose intensity / Planned dose intensity. Actual dose intensity (mg/day) is defined as Actual cumulative dose received (mg) / Duration of exposure (days). Planned dose intensity (mg/day) is defined as Planned cumulative dose (mg) / Duration of exposure (days).

Program: (Program name.sas) (run on: DDMMYYYY HH:MM)

Filename: (Specify file name.rtf)

BioMed Valley Discoveries  
Protocol: BVD-523-ABC ('Delivery' / 'Type') - Part X  
Data extraction date: DDMMYYYY

Page 1 of Y

Table 14.1-4.2 - Dosing Interruptions and Adjustments  
Full Analysis Set

	Group 1 N=XX n (%)	Group 2 N=XX n (%)	Group 3 N=XX n (%)	Group 4 N=XX n (%)	Group 5 N=XX n (%)	Group 6 N=XX n (%)	Overall N=XX n (%)
At least one dose change - n (%)	XX (XX.X)						
Reason dose changed - n (%) [a]							
Adverse event	XX (XX.X)						
Parental/Guardian decision	XX (XX.X)						
Consent withdrawal	XX (XX.X)						
...	XX (XX.X)						
Other							
Dose changed to - n (%) [b]							
150mg BID	XX (XX.X)						
300mg BID	XX (XX.X)						
450mg BID	XX (XX.X)						
600mg BID	XX (XX.X)						
At least one dose interruption - n (%)	XX (XX.X)						
Reason dose interrupted [a]							
Adverse Event	XX (XX.X)						
Dispensing Error	XX (XX.X)						
Investigator Decision	XX (XX.X)						
Consent Withdrawal	XX (XX.X)						
Patient Decision	XX (XX.X)						
Other	XX (XX.X)						

[a] A patient can be counted under several reasons if they had multiple different dose changes/interruptions.

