**PROGRAMMING NOTES:**

- Repeat Table 14.3-1.12
- Add footnote:  
“TEAEs leading to treatment discontinuation: any TEAEs with Action taken with study treatment=Drug withdrawn within the first 28 days of study.”

Table 14.3-1.15 – Summary of Related Treatment-Emergent Adverse Events Leading to Treatment Discontinuation Within Cycle 1  
Safety Analysis Set

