**Statistical Analysis Plan:**

2.0 / 09-Jun-2023

BioMed Valley Discoveries  
Protocol: BVD-523-ABC ('Delivery' / 'Type') - Part X  
Data extraction date: DDMMYYYY

Page 1 of Y

Listing 16.2.5-3 - Drug Exposure  
Full Analysis Set

Group: Group 1

Subject ID	Age / Gender	Number of cycles received [a]	Duration of exposure (months) [b]	Planned cumulative dose (mg)	Actual cumulative dose received (mg) [c]	Relative dose intensity [d]
xxx-xx	xx/M	xx	xxx	xxx (mg)	xxx (mg)	xxx
xxx-xx	xx/F	xx	xxx	xxx (mg)	xxx (mg)	xxx

Note: M=Male, F=Female.

[a] Number of cycles received = Number of cycles where the patient received at least one dose.

[b] Duration of exposure (months) = (Date of last known treatment dosing with ulixertinib- date of initial dosing with ulixertinib) + 1 / 30.4375.

[c] Actual cumulative dose received (mg) = Sum of [(number of capsules dispensed - number of capsules returned) x 150].

[d] Relative dose intensity = 100 x Actual dose intensity / Planned dose intensity. Actual dose intensity (mg/day) is defined as Actual cumulative dose received (mg) / Duration of exposure (days). Planned dose intensity (mg/day) is defined as Planned cumulative dose (mg) / Duration of exposure (days).

Program: (Program name.sas) (run on: DDMMYYYY HH:MM)

Filename: (Specify file name.rtf)

**Sponsor:** BioMed Valley Discoveries

**Protocol:** BVD-523-ABC

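### Relative dose intensity in SAP 9.6 charges every started cycle at its full 28-day dose, so a patient who takes every dose but stops part-way through a cycle scores below 100% (last dose day 10: 35.7%; day 42: 75.0%)

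*SAP*

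**What the plan says.** SAP 9.6 (Part A) builds RDI in four steps.

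- Cycles received: "Number of cycles where the patient received at least one dose".
- Planned cumulative dose in mg: "Number of cycles received x 28 x 2 x 600".
- Actual cumulative dose: capsules dispensed minus capsules returned, times 150 mg.
- Intensities: each cumulative dose is divided by duration of exposure, for example "Planned dose intensity (mg/day) = Planned cumulative dose (mg) / Duration of exposure (days)". RDI is 100 times the ratio of the two.

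Duration of exposure runs from first to last dose, inclusive, so it ends at the last dose and not at the end of the cycle. The footnotes of the Table 14.1-4.1 shell repeat the definition ("Relative dose intensity = 100 x Actual dose intensity / Planned dose intensity"), as does the shell of Listing 16.2.5-3, Drug Exposure ("Planned dose intensity (mg/day) is defined as Planned cumulative dose (mg) / Duration of exposure (days)"). Neither document pro-rates the last cycle. The list of outputs marks both the table and this listing for the final analysis, which SAP 7.2 says will feed an abbreviated, safety-focused report.

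**The concern.** The text describes an intensity, a dose per day compared with a planned dose per day. The formula does not deliver one. Numerator and denominator share the same number of days, so the days drop out and what remains is the fraction taken of the full dose of all started cycles.

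Treatment stops when an event occurs (progression, toxicity, study closure; SAP 6.1), and nothing ties the stop to the end of a cycle. Early termination of the study adds stops that may have no connection with tolerability. A patient who stops mid-cycle after taking every dose is charged for the days after stopping, and RDI falls as though doses had been reduced or missed. In a report centred on safety, RDI will be read as a measure of how well the scheduled dose was maintained. As defined, it mixes that with the timing of the last dose.

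**Working it through.** The plan states no RDI value, so there is no figure of its own to reproduce. The check applies the SAP 9.6 formulas directly.

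**Inputs from the documents**
- Scheduled dose: 600 mg twice daily in 28-day cycles (SAP 6.2; Protocol 8.1.2), so 2 x 600 = 1,200 mg/day.
- Planned dose per started cycle: 28 x 2 x 600 = 33,600 mg (SAP 9.6).
- Capsule strength: 150 mg (Protocol 8.2.2; SAP 9.6).

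**Assumptions for illustration**
- The stopping days are chosen here; the documents give none.
- Every dose is taken and all unused capsules are returned.
- Cycles last their nominal 28 days. Moving the start of Cycle 2 anywhere in days 26-32, or of Cycle 3 in days 54-60, does not change the number of cycles counted for last doses on days 10, 14, 42 and 70.

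**Formula.** Let L be the last dose day, c the cycles counted and A the mg taken.

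RDI = 100 x (A/L) / (33,600c/L) = 100 x A / (33,600c)

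L has cancelled. With full dosing A = 1,200L, so RDI = 100 x L / (28c).

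| Last dose day | Cycles counted | Actual mg | Planned mg | Planned intensity, mg/day | RDI |
|---|---|---|---|---|---|
| 10 | 1 | 12,000 | 33,600 | 3,360 | 35.7% |
| 14 | 1 | 16,800 | 33,600 | 2,400 | 50.0% |
| 28 | 1 | 33,600 | 33,600 | 1,200 | 100.0% |
| 42 | 2 | 50,400 | 67,200 | 1,600 | 75.0% |
| 70 | 3 | 84,000 | 100,800 | 1,440 | 83.3% |
| 154 | 6 | 184,800 | 201,600 | 1,309 | 91.7% |

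Days 14, 42, 70 and 154 are all half-way through a cycle. The shortfall falls from 50.0 points in cycle 1 to 8.3 points in cycle 6.

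**Two different histories, one RDI**
- Full dose to day 42: 50,400 / 67,200 = 75.0%. An average of 450 mg twice daily for 56 days: 900 x 56 = 50,400 mg, and 50,400 / 67,200 = 75.0%.
- Full dose to day 14: 16,800 / 33,600 = 50.0%. An average of 300 mg twice daily for 28 days: 600 x 28 = 16,800 mg, and 16,800 / 33,600 = 50.0%.

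**With planned dose = 1,200 mg x days of exposure**
- Every row of the table becomes 100%, for example 12,000 / 12,000 and 50,400 / 50,400.
- The reduced-dose patients stay at 75.0% (50,400 / 67,200) and 50.0% (16,800 / 33,600).

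**The case against.** Four objections deserve weight.

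1. *This is a definition, not a miscalculation.* The SAP may intend a measure of dose delivered against the full dose of started cycles, and no stated figure is wrong. That is fair, and such a ratio is legitimate. What stands is that the SAP calls it a dose intensity in mg/day, and its planned value is 3,360 or 1,600 mg/day where its own schedule gives 1,200.

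2. *Nobody is declared under-dosed.* A reader might infer that the plan classifies early stoppers as under-dosed. It does not: no RDI threshold appears anywhere, and Table 14.1-4.1 shows only n, mean (SD), median, minimum and maximum. The point concerns what those summaries convey.

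3. *Other outputs resolve the ambiguity.* Listing 16.2.5-3 (Drug Exposure) prints cycles, duration, planned and actual mg and RDI in one row. Full dose to day 14 shows 14 / 30.4375 = 0.46 months; the 28-day patient at half dose shows 28 / 30.4375 = 0.92 months. Dose changes, interruptions and reasons for stopping are also reported. This holds patient by patient, but none of it corrects the RDI summaries in the table.

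4. *A new denominator has its own weakness.* Ending exposure at the last dose ignores a final hold that runs into discontinuation, and unreturned capsules can push RDI above 100%. Both are true, and the fix has to deal with them.

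A reader might also infer that RDI is erratic at cycle boundaries because SAP 9.6 does not say how cycle starts are dated. The documents do not establish that: SAP 7.7 analyses data by planned visit as collected in the eCRF, without reassignment by date. The point does not need it.

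**Conclusion.** The RDI definition in SAP 9.6 does not measure what its label says, and it should be changed. For a patient with no missed or reduced doses, RDI is the fraction used of the calendar days in all started cycles. It gives 35.7% at day 10, 50.0% at day 14, 75.0% at day 42 and 83.3% at day 70, where dosing against schedule was 100%.

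The limits are clear. A full-dose patient whose last dose falls on the last day of a cycle gets 100%. The shortfall shrinks as cycles accumulate. The figures assume unused capsules are returned; unreturned capsules raise the actual dose and can mask the effect. The documents do not say how many patients stop mid-cycle, so the effect on the tabulated mean cannot be estimated from them.

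A reader might infer that the trial's efficacy conclusions are affected. They are not: RDI is descriptive, is not an endpoint and enters no test. The case for acting is that the safety-focused report will carry a misleading exposure summary that is cheap to correct.

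**What to change.** - **Redefine the denominator.** For RDI, take planned cumulative dose as 2 x 600 mg x duration of exposure in days (last dose date - first dose date + 1). The page 2 footnote of Table 14.1-4.1 already uses this day count ("Duration of exposure (days) = (Date of last known treatment dosing with ulixertinib" and so on). Planned dose intensity is then 1,200 mg/day for everyone, and held days between first and last dose stay in the denominator.
- **Keep the present ratio as a second row**, relabelled *percent of full planned dose of started cycles*. This keeps a final hold visible without a conditional end date. A patient dosed on days 1-10, held for 21 days and discontinued on day 32 would show RDI 100% and 35.7% on the second row, the same as a patient who stops outright on day 10. Ending exposure at discontinuation only when a hold came first would give 12,000 / (32 x 1,200) = 31.3% against 100% for identical doses taken.
- **Handle unreturned capsules.** A day-10 stopper who returns nothing from a full cycle's supply would show 33,600 / 12,000 = 280%, against 100% under the present formula. Identify such patients in the Drug Exposure listing and summarise RDI in the table with and without them. A flag in the listing alone would not protect the table's mean and maximum.
- **Update the footnotes** of Table 14.1-4.1 (page 1 gives duration in months, page 2 in days) and of Listing 16.2.5-3 (Drug Exposure), where the month formula lacks the outer brackets. State which planned dose the listing column shows.

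The cost is one formula, one relabelled row, one repeated summary and the footnotes. The data come from fields already in the shells: dose dates, capsule counts and the reason capsules were not returned. That reason appears in Listing 16.2.5-4, which is not marked for final delivery, so the Drug Exposure listing must carry the identification. No dosing rule changes.

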## 9.7 PHARMACOKINETIC/ PHARMACODYNAMIC ENDPOINTS AND ANALYSES

### 9.7.1 Pharmacokinetic Data

Blood samples will be collected when the patient is at steady state (patients who have received at least 5 days, or 10 consecutive doses, of investigational product) to measure ulixertinib and selected metabolites plasma concentrations. Plasma concentration will be listed and summarized by analyte and visit including the Geometric mean and Coefficient of Variation. All data will be listed but tables will only include data that was collected when ulixertinib was at steady state as required by protocol.

### 9.7.2 Pharmacodynamic Data

Blood samples will be collected pre-dose and 4 hours +/- 10 minutes post-dose on cycle 1 day 1, and cycle 1 day 15 to measure phosphorylation of ERK1/2 target RSK (pRSK). Percent inhibition of pRSK compared to baseline will be listed and summarized.

## 9.8 EFFICACY DATA ENDPOINTS AND ANALYSES

All efficacy analyses will be performed on the FAS and replicated on PP and EAS as supportive analysis for Part B. For Part A only FAS and EAS will be used for efficacy analysis.

All efficacy data will be presented by group and overall, for both Part A and Part B, unless otherwise specified in the specific section.

### 9.8.1 Overall Response Rate (ORR) / Best Overall Response (BOR)

Tumor response will be assessed by the Investigator using RECIST 1.1 criteria.

The decision for body areas to be scanned will depend on the extent of disease. Tumor assessments must include all known or suspected disease sites. Imaging will be performed on the abdomen, chest, pelvis, and the site of the primary tumor if elsewhere. Tumor measurements based on physical examination will occur at baseline and on the first day of each treatment cycle.

Tumor assessments will be made by CT/MRI/Physical Exam prior to dose initiation, at the 1st protocol-specified tumor measurement evaluation at the beginning of Cycle 2 and then every 2 cycles, and at End of Treatment. Patients that discontinue study treatment for any reason other than disease progression, must continue to have disease assessments every 8 weeks ( $\pm$  7 days) until disease progression or the initiation of subsequent anticancer therapy. The schedule of tumor assessments should be fixed according to the calendar, starting with cycle one day one, regardless of treatment delays or interruptions due to toxicity. The same imaging technique used to characterize each identified and reported lesion at baseline will be employed in the following tumor assessments.

Anatomical measurements (target lesions) will be documented during screening and each subsequent evaluation. Objective assessments will be performed during screening and before the first study drug dose of every other cycle, starting with cycle 2.

The table below provides a summary of the overall response status determination at each time point.

**Table 5. Evaluation of Overall Response**

Target lesions	Non-target lesions	New lesions	Overall response
CR	CR (or no non-target lesions)	No	CR
No target lesion a	CR	No	CR
CR	NE b	No	PR
CR	Non-CR/non-PD	No	PR
PR	Non-PD and NE (or no non-target lesions) b	No	PR
SD	Non-PD and NE (or no non-target lesions) b	No	SD
Not all evaluated	Non-PD	No	NE
No target lesion a	Not all evaluated	No	NE
No target lesion a	Non-CR/non-PD	No	Non-CR/non-PD
PD	Any	Yes or No	PD
Any	PD	Yes or No	PD
Any	Any	Yes	PD
No target lesion a	Unequivocal PD	Yes or No	PD
No target lesion a	Any	Yes	PD

CR = complete response, PR = partial response, SD = stable disease, PD = progressive disease, and NE = not evaluable.

aDefined as no target lesion at baseline.

bNot evaluable is defined as when either no or only a subset of lesion measurements is made at an assessment.

The ORR is defined as the percentage of patients having a confirmed response of either CR or PR. ORR will be calculated with the 95% confidence intervals (CIs). The 95% CIs will be estimated using the Clopper-Pearson method.

For Part B, ORR will be compared between ulixertinib and physician's choice of treatment using a Chi square test or Fisher's exact test as applicable.

Complete and partial response must be confirmed by a repeat assessment performed at > or = 4 weeks after the criteria for response are first met. Date of confirmed CR/PR will be the date of the first CR/PR that qualifies for confirmation. Additionally, patients with no post-baseline efficacy measurement due to reasons accountable for disease progression, will be assessed as non-evaluable and will count in the denominator of the ORR.

BOR will be assessed based on the tumor response at different evaluation time points from baseline until the first documented disease progression for RECIST or the last response assessment if there is no document disease progression at the time of the analysis. The order used to determine BOR is CR>PR>SD>PD, ignoring visits with missing tumor assessments. For SD to qualify for BOR, the SD assessment should be at least 6 weeks after first ulixertinib dose. BOR

date in this case will be the date of the first SD/PR/CR documented after 6 weeks.

The following table, based on Table 3 from the RECIST 1.1 guidelines, summarizes the algorithm describing how confirmed response and BOR are determined from the overall tumor assessments.

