10.1.9 Disease Status

The decision for body areas to be scanned will depend on the extent of disease. Disease assessments must include all known or suspected disease sites. Imaging will be performed on the abdomen, chest, pelvis, and the site of the primary tumor if elsewhere.

Tumor measurements based on physical examination will occur at baseline and on the first day of each treatment cycle. Tumor assessments will be made by CT/MRI/Physical Exam prior to dose initiation, at the 1st protocol-specified tumor measurement evaluation at the beginning of Cycle 2 and then every 2 cycles, and at End of Treatment. Patients that discontinue study treatment for any reason other than disease progression, must continue to have disease assessments every 8 weeks (\pm 7 days) until disease progression or the initiation of subsequent anticancer therapy. The schedule of tumor assessments should be fixed according to the calendar, starting with cycle one day one, regardless of treatment delays or interruptions due to toxicity. The same imaging technique used to characterize each identified and reported lesion at baseline will be employed in the following tumor assessments.

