**Table 2. Analysis periods**

Phase	Period	Definition
Part A and Part B	PRE-TREATMENT	From informed consent form (ICF) signature to the day before first dose of study treatment.
	ON-TREATMENT	From the day of first dose of study treatment to ≤14 ± 3 days after last dose of study treatment (date of EOT visit), or the earliest date of subsequent anti-cancer drug therapy – 1 day, whichever occurs first.
	FOLLOW-UP	From day ≤14 ± 3 after last dose of study treatment, or the earliest date of subsequent anti-cancer drug therapy, whichever occurs first, to end of study. End of study is date of completion / discontinuation from the study as collected in the CRF or the last recorded assessment in the database if the patient has not completed/discontinued the study at the time of the analysis.

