#### 9.8.2 Duration of Response (DOR)

The duration of response (in months) is defined as the period from the date of initial confirmed PR or CR until the date of first radiographically documented progressive disease or death from any cause. Only patients with BOR of CR or PR (i.e. responders) will be included in the analysis of duration of response.

$$DOR = [(Date of first PD/death - Date of first recorded confirmed CR/PR) + 1] / 30.4375$$

Patients with no documented progression or death after CR or PR will be censored at the last available tumor assessment (last assessment that is CR, PR, or SD):

$$DOR = [(Date of last assessment - Date of first recorded CR/PR) + 1] / 30.4375$$

The analysis of DOR will be performed with a Kaplan-Meier method (product-limit estimates) and a summary of associated statistics will be presented including corresponding two-sided 95% CI. The CI for the median will be calculated according to Brookmeyer and Crowley and CI for the survival function estimates at Month 3, 6, 9, 12, and 18 will be derived using the log-log transformation (SAS PROC LIFETEST CONFTYPE=LOGLOG), only if there are sufficient data for responders. However, the final choice of timepoints may be updated dependent upon the data.

Part B, DOR will be compared between ulixertinib and physician's choice of treatment using a Log Rank test or other appropriate test if the proportional hazards assumption does not hold.

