### 9.8.3 Progression-free Survival (PFS)

The PFS (in months) is defined as the time from the first ulixertinib dose until the first radiographically documented progression of disease or death from any cause, whichever occurs first.

$$PFS = [(Date of first PD/death - Date of first study treatment) + 1] / 30.4375$$

Patients with no documented progression or death will be censored at the last available tumor assessment (last assessment that is CR, PR or SD):

$$PFS = [(Date of last assessment where patient is PD free - Date of first study treatment) + 1] / 30.4375$$

For patients with no post baseline tumor assessment a censored PFS at day 1 will be considered.

$$PFS = (Date of first study treatment - Date of first study treatment) + 1$$

The analysis of PFS will be performed with a Kaplan-Meier method (product-limit estimates) and a summary of associated statistics will be presented including corresponding two-sided 95% CI. The CI for the median will be calculated according to Brookmeyer and Crowley and CI for the survival function estimates at Month 3, 6, 9, 12, and 18 will be derived using the log-log transformation (SAS PROC LIFETEST CONFTYPE=LOGLOG). However, the final choice of timepoints may be updated dependent upon the data.

For Part B, for each histology, PFS curves will be compared between ulixertinib and physician's choice of treatment using Log Rank Test or other appropriate test if the proportional hazards assumption does not hold.

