**Statistical Analysis Plan:**

2.0 / 09-Jun-2023

BioMed Valley Discoveries  
 Protocol: BVD-523-ABC ('Delivery' / 'Type') - Part X  
 Data extraction date: DDMMYYYY

Page 1 of Y

Listing 16.2.6-7 - Survival Status  
 Full Analysis Set

Group: Group 1

Subject ID	Age/ Gender	Completed End of Study?	Any Anti-Cancer Treatment Since End of Study or Last FUP/ Start Date	Any Tumor Assessment Since End of Study or Last FUP/ Assessment Date/ Overall Response	Survival Status at Follow-Up	Date of Death	Last Known Date Patient Alive [a]
xxx-xx	xx/M	Yes	Yes/ DDMMYYYY	Yes/ DDMMYYYY/ Complete Response	Alive		
xxx-xx	xx/F	Yes	No	No	Dead	DDMMYYYY	

Note: M=Male, F=Female, FUP=Follow-up, CR=Complete Response, Non CR/Non PD=Non Complete Response/Non Progressive Disease, PR=Partial Response, SD=Stable Disease, PD=Progressive Disease, NE=Not Evaluable.  
 [a] If Survival status at the time of follow-up is unknown.

Program: (Program name.sas) (run on: DDMMYYYY HH:MM)

Filename: (Specify file name.rtf)

**Sponsor:** BioMed Valley Discoveries

**Protocol:** BVD-523-ABC

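### The response window has no cut at subsequent anticancer therapy or crossover, so a response reached or confirmed on the next drug can count in ORR; PFS handling of such switches needs a sensitivity analysis.

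*SAP*

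**What the plan says.** **Response.** SAP 9.8.1, in the text under Table 5, takes BOR from assessments "from baseline until the first documented disease progression for RECIST or the last response assessment if there is no document disease progression". ORR is the share of patients whose confirmed response is CR or PR. Confirmation needs a repeat assessment at least 4 weeks later. Neither rule mentions subsequent therapy or crossover.

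**PFS and DOR.** SAP 9.8.3 runs PFS "until the first radiographically documented progression of disease or death from any cause, whichever occurs first", and "Patients with no documented progression or death will be censored at the last available tumor assessment". SAP 9.8.2 runs DOR "until the date of first radiographically documented progressive disease or death from any cause", and "Patients with no documented progression or death after CR or PR will be censored at the last available tumor assessment". Protocol 11.5.5 has the same structure. The protocol synopsis adds only that censoring will be applied where appropriate.

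**Collection.** Patients who stop the drug without progression are scanned every 8 weeks "until disease progression or the initiation of subsequent anticancer therapy" (Protocol 10.1.9; also 9.4, 10.3.7 and SAP 9.8.1 itself). Survival follow-up continues to 18 months from the start of study therapy (Protocol 9.4).

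**What may be in the database.** Shell Listing 16.2.6-7 (Survival Status) shows any new anticancer treatment with its start date. The next column is "Any Tumor Assessment Since End of Study or Last FUP/ Assessment Date/ Overall Response".

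**Where the SAP does make the cut.** Table 2 in SAP 7.3 ends the on-treatment period the day before "the earliest date of subsequent anti-cancer drug therapy". That period serves adverse events and concomitant medication. Section 9.8 does not use it.

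**The concern.** Part A has no control arm, so a response obtained on a later drug is simply added to ulixertinib's ORR, and nothing offsets it. Two programmers could treat the same switching patient differently and both comply with the SAP.

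The easier route is confirmation. A patient with a first PR on ulixertinib stops for toxicity, starts another drug, and has one further scan showing PR at least 28 days after the first. Table 6, case 7, makes this a confirmed PR.

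In Part B the protocol allows crossover when a patient progresses on physician's choice, while the primary PFS and one version of ORR rest on independent review. If the independent review did not call the progression that led to crossover, the control patient's window stays open, and scans taken on ulixertinib count for the control arm.

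For PFS, a patient who switches without progression has no required scans afterwards but remains under survival follow-up. A later death becomes the PFS event, at the death date.

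**Working it through.** No sample size, power or alpha figure in the plan depends on this rule, so there is no stated figure to reproduce. The check has four steps.

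**1. Do any of the rules stop at a switch?**

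| Rule | Ends at progression | Ends at new therapy |
|---|---|---|
| BOR/ORR window (SAP 9.8.1) | yes | no |
| DOR, PFS events and censoring (SAP 9.8.2, 9.8.3) | yes | no |
| Required scans (SAP 9.8.1, Protocol 10.1.9) | yes | yes |
| Survival follow-up (Protocol 9.4) | no | no |
| On-treatment period (SAP Table 2) | not applicable | yes |

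The only analysis rule with the cut is one that the efficacy section does not use.

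**2. Size for ORR.** One extra responder adds 100/n points: 100/34 = 2.9 and 100/38 = 2.6. In a group that closed smaller because of early termination, the step is larger.

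As an illustration, take a true ORR of 20% (the null value in SAP 6.4). Assume that a share f of non-responders switch before PD and have qualifying scans recorded, and that a share q of these respond on the next drug. Then observed ORR = 0.20 + 0.80 × f × q. The smallest count with an exact one-sided tail of at most 5% at n = 34 is 12 responders (actual alpha 2.7%).

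| f | ORR, q = 20% to 30% | Chance of at least 12 of 34 |
|---|---|---|
| 0% | 20.0% | 2.7% |
| 5% | 20.8% to 21.2% | 3.6% to 4.2% |
| 10% | 21.6% to 22.4% | 4.7% to 6.0% |
| 20% | 23.2% to 24.8% | 7.6% to 11.4% |

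Both f and q are assumptions. If no post-switch scans are recorded, f is zero and ORR is unaffected.

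**3. PFS for one constructed patient.** SD on day 29, new drug on day 60 without PD, death on day 400.
- As written: 400/30.4375 = 13.1 months, event.
- Censored at the last scan before the switch: 29/30.4375 = 0.95 month.

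**4. PFS for a group (simulation; every input assumed).** Exponential PFS with a 3-month median; scans on days 29, 85, 141 and every 56 days after; switch times uniform over days 15 to 90; median survival after the switch 9 months; deaths counted to day 548. With no switching, 3-month PFS on this scan grid is 0.5^(85/91.3) = 0.525 and the Kaplan-Meier median falls at the 4.63-month scan.

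| Who switches | Share switching | As written | Censored at last prior scan |
|---|---|---|---|
| Only the truly progression-free | 14% | 0.529 | 0.504 |
| Only the truly progression-free | 20% | 0.531 | 0.490 |
| Anyone without documented PD | 17% | 0.553 | 0.525 |
| Anyone without documented PD | 37% | 0.591 | 0.524 |

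Against 0.525, the written rule reads up to about 1 point high in the first case and about 3 to 7 points high in the second. Censoring reads about 2 to 3.5 points low in the first case and is unbiased in the second.

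**The case against.** The strongest reply is that the ORR route is mostly closed.
- Required scans stop at new therapy, and SAP 9.8.1 says so itself.
- SAP 7.8 keeps unscheduled assessments out of summaries other than baseline, worst on-treatment safety results and time-to-event analyses, unless otherwise specified.
- Under Table 6, case 11, SD followed by a single PR or CR stays SD. A patient with no response before the switch would need two qualifying scans on the next drug.
- The follow-up tumor-assessment column is needed anyway for patients who stop without progression and start nothing new.

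This stands as a limit on frequency. A reader might infer from the missing cut that next-drug responses are routinely credited to ulixertinib; the documents do not support that. It does not close the gap. Disease assessment in follow-up is itself a scheduled item in the Schedule of Activities, so a scan on the follow-up form need not be classed as unscheduled. One such scan is also enough to confirm an earlier PR.

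On PFS, counting later deaths follows the definition, which includes death from any cause, and censoring has its own bias, as step 4 shows. That stands. It is why censoring belongs in a sensitivity analysis and not as a required primary rule.

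A reader comparing the two rules might also infer that the written one pushes median PFS from the 2.8-month to the 4.6-month scan. It does not: 4.63 months is also the no-switching median, and the 2.8-month value comes from censoring when only truly progression-free patients switch.

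Finally, the study ended early in Part A with a safety-focused report, DOR outputs are not marked for the final analysis, and Part B is deferred to a later SAP. These points narrow the consequences to the Part A ORR and PFS outputs, which are marked for delivery.

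**Conclusion.** The point holds for response. The BOR/ORR window has no cut at subsequent therapy or crossover, and data from after a switch can be in the database. A response reached or confirmed on another drug can therefore enter the primary endpoint, at 2.6 to 2.9 points per patient for groups of 38 or 34. How often this happens cannot be derived from the documents; it could be never.

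For PFS, and for DOR if it is produced, the point is narrower. Deaths after a switch without progression are counted, with no required scans in between. This is a permissible choice whose effect is not visible in the planned outputs. The range of roughly 1 to 7 points on 3-month PFS rests wholly on assumed switching rates, switching mechanism and survival. No claim about the median is supported. The Part B limb is conditional on that part being run and on the independent review disagreeing with the progression call behind crossover. The change should be made, but it does not undermine the design.

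**What to change.** - **SAP 9.8.1:** limit BOR, ORR and response confirmation to assessments up to the first of progression, start of subsequent anticancer therapy, or (Part B) crossover.
- **SAP 9.8.3, and 9.8.2 if DOR is produced:** keep the progression-or-death definition if the sponsor prefers it, and say explicitly that events after subsequent therapy count. Add a sensitivity analysis censoring at the last evaluable assessment before subsequent therapy or crossover, when neither progression nor death came first.
- **Reporting:** give, by group, the number of patients who started subsequent therapy without documented progression and the number of those who then died. State that the censored analysis can read low if the patients who switch are those still free of progression.

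The cost is a few sentences, one derived date and one extra PFS analysis. The therapy start date is already in Listing 16.2.6-7. The downside is that ORR may come out slightly less favourable. Because SAP 2.0 is final, the change belongs in the SAP change log and the study report, as Protocol 11.7 provides. The crossover wording can wait for the Part B SAP.
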